5.2 Randomized Portion

The Randomized Portion of this study will only proceed if there have been 10 evaluable patients on the Pilot Portion (this includes both full dose glyburide and reduced dose glyburide, if applicable) and it is deemed safe. All data will be reviewed and approved by the Data Safety Monitoring/Quality Assurance Committee (DSMQAC) after the Pilot Portion and prior to starting the Randomized Portion at the safe dose as determined by the Pilot Portion. The Randomized Portion will enroll 40 evaluable patients. Inevaluable patients will be replaced.

Patients with brain metastases, who are not taking dexamethasone (or any other corticosteroid with the purpose of treating cerebral edema) within 5 days prior to SRS, after informed consent, will be randomized to a blinded investigational medication:

- Non-Micronized glyburide (1.25 mg po BID) should begin at least 5 days prior to SRS to be taken until the evening dose on the day of the one month follow-up MRI.
OR
- Placebo (1 tablet po BID) should begin at least 5 days prior to SRS to be taken until the evening dose on the day of one month follow-up MRI.

All patients will receive linac-based radiosurgery, which must be initiated at least 5 days after starting the investigational medication (can be more for patients being treated with linac-based radiosurgery where the MRI may be done within 21 days prior to SRS treatment).

For treatment planning and at the time of the one and three month follow-up appointments, the patient must undergo a brain MRI with and without contrast. T1-weighted, T2, and/or

FLAIR MRI of the brain (maximum slice thickness 5mm). FLAIR imaging is preferred. The treatment planning MRI may be done within 21 days prior to SRS treatment only for patients being treated with linac-based radiosurgery where it is not standard of care to complete a MRI on the day of SRS (as it is with gamma knife).

T1 post-gadolinium sequences and FLAIR axial sequences from the treatment planning MRI (see note above regarding linac-based radiosurgery patients) and at the one and three month follow-up appointments will be imported into the Eclipse treatment planning system. On the T1 post gadolinium sequences, the radiation oncologist will contour the enhancing tumor that received the prescribed dose of SRS. Using the FLAIR sequences Eclipse will automatically calculate FLAIR volume using “Region Growing” (Appendix I). The automated contours will be verified and modified as needed by the radiation oncologist. Physicians, patients, and the study team will be blinded to the patient’s investigational medication.

5.2.1 Patients can only be enrolled after all eligibility criteria are met. The date of registration/enrollment/study entry is considered to be the day the Eligibility Checklist is signed by the verifying physician and should be no later than 5-9 days prior to SRS. Once a patient is enrolled, a unique case number will be assigned to the patient and blinded randomization will occur. Patients will be randomized by the UAB Investigational Drug Services (IDS) Pharmacy, who will hold the blind for this study.

5.3 Definition of Dose Limiting Toxicity (DLT)

5.3.1 Pilot Portion

All adverse events and toxicities will be graded and reported according to the revised NCI Common Terminology Criteria for Adverse Events (CTCAE) version 4.0. The CTCAE version 4.0 is located on the CTEP website at

http://ctep.cancer.gov/protocolDevelopment/electronic_applications/ctc.htm. See

Appendix VII for Adverse Event (AE) definitions and grading scale information.

If multiple toxicities are seen, the presence of a DLT should be based on the most severe toxicity experienced. Any patient who achieves a DLT will be taken off of glyburide immediately, but will still be evaluable.

Concerning Toxicity

1. Any **asymptomatic grade 3 or 4 hypoglycemia** as defined by CTCAE version 4.0.
2. Any **non-hematologic grade 3 or greater toxicity** (including neurologic toxicity) that is associated with a blood glucose level ≤ 80 mg/dl and is resolved with “low blood sugar intervention” (e.g. a return of blood glucose level to ≥ 80 mg/dl). **See Section 5.4.1.1 for a List of Low Blood Sugar Interventions.**

Serious Toxicity

1. Any **grade 5 toxicity** that is deemed by the investigator to be **at least possibly attributable to glyburide**.
2. Any **symptomatic grade 3 or 4 hypoglycemia associated with a non-hematologic grade 3 or greater toxicity** that is not resolved with “low blood sugar intervention” (e.g. does not

return to blood glucose level to ≥ 80 mg/dl) that is deemed by the investigator to be at least possibly attributable to glyburide. **See Section 5.4.1.1 for a List of Low Blood Sugar Interventions.**

Glyburide will be discontinued for any patient that meets the criteria for either a "**concerning toxicity**" or "**serious toxicity**". These patients will still be evaluable.

Any "**concerning toxicity**" that is observed in at least 6 (of 10 evaluable) patients will trigger a dose reduction (see section 7.1). After 1 dose reduction, if at least 6 (of 10 evaluable) patients are observed to have a "**concerning toxicity**", the study will be terminated.

Any "**serious toxicity**" that is observed in at least 1 (of 10 evaluable) patients will trigger a dose reduction. After 1 dose reduction, if at least 1 (of 10 evaluable) patients is observed to have a "**serious toxicity**", the study will be terminated.

5.3.1.1 If a dose reduction should occur, it will occur once the pre-specified DLT is reached.

Glyburide will be reduced to 0.75 mg po BID. In the event this dose reduction should occur, the Pilot Portion will be performed using the reduced dose (e.g. 10 evaluable patients are required to be assessed). If another DLT is observed at the reduced glyburide dose warranting a dose reduction, the study will be terminated.

5.3.1.2 The patient who experiences a DLT (e.g. either a "**concerning toxicity**" or "**serious toxicity**") will stop glyburide immediately, but will still be evaluable. If the DLT is a "**concerning toxicity**", all other patients currently on treatment at the time may continue at their current glyburide dose. If the DLT is a "**serious toxicity**", all other patients currently on treatment will either be dose reduced immediately (if on full dose glyburide) or stop glyburide immediately (if on reduced dose glyburide). All other patients will still be evaluable.

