2.3 Primary Endpoints

2.3.1 Pilot Portion: Occurrence of Dose Limiting Toxicities (DLTs) between the time of glyburide initiation and the time of the one month follow-up MRI.

2.3.2 Randomized Portion: Occurrence of edema increase and initiation of dexamethasone (or any corticosteroid administration with the purpose of treating cerebral edema) between the time of SRS* and the time of the one month follow-up MRI.

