4.1.9 Conditions for early patient stopping of glyburide

- 4.1.9.1** A dose limiting toxicity (DLT) is reached. See section 5.3.1.
- 4.1.9.2** Patient requires corticosteroid administration after registration but prior to SRS, please note these patients will be deemed inevaluable.

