4.2.9 Conditions for early patient stopping of investigational medication

4.2.9.1 A dose limiting toxicity (DLT) is reached. See section 5.3.2.

4.2.9.2 Patient requires corticosteroid administration after registration but prior to SRS, please note these patients will be deemed inevaluable.

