Appendix VII for Adverse Event (AE) definitions and grading scale information.

If multiple toxicities are seen, the presence of a DLT should be based on the most severe toxicity experienced. Any patient who achieves a DLT will be taken off of the investigational medication immediately, but will still be evaluable.

Concerning Toxicity

1. Any **asymptomatic grade 3 or 4 hypoglycemia** as defined by CTCAE version 4.0.
2. Any **non-hematologic grade 3 or greater toxicity** (including neurologic toxicity) that is associated with a blood glucose level ≤ 80 mg/dl and is resolved with "low blood sugar intervention" (e.g. a return of blood glucose level to ≥ 80 mg/dl).

Serious Toxicity

1. Any **grade 5 toxicity** that is deemed by the investigator to be **at least possibly attributable to the investigational medication**.
2. Any **symptomatic grade 3 or 4 hypoglycemia** that is associated with a **non-hematologic grade 3 or greater toxicity** that is not resolved with “low blood sugar intervention” (e.g. does not return to blood glucose level of ≥ 80 mg/dl) that is deemed by the investigator to be **at least possibly attributable to the investigational medication**.

Investigational medication will be discontinued for any patient that meets the criteria for a “concerning toxicity” or “serious toxicity”. These patients will still be evaluable. All other patients currently on treatment at the time may continue with their current investigational medication without interruption.

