7.3.4 Grading Toxicities and Adverse Events

The descriptions and grading scales found in the revised NCI Common Terminology Criteria for Adverse Events (CTCAE) version 4.0 will be utilized for adverse event reporting on this study. The CTCAE version 4.0 is located on the CTEP website at http://ctep.cancer.gov/protocolDevelopment/electronic_applications/ctc.htm. See Appendix VII for Adverse Event (AE) definitions and grading scale information.

PILOT PORTION

If multiple toxicities are seen, the presence of a DLT should be based on the most severe toxicity experienced. Any patient who achieves a DLT will be taken off of glyburide immediately, but will still be evaluable.

Concerning Toxicity

1. Any asymptomatic grade 3 or 4 hypoglycemia as defined by CTCAE version 4.0.
2. Any non-hematologic grade 3 or greater toxicity (including neurologic toxicity) that is associated with a blood glucose level ≤ 80 mg/dl and is resolved with “low blood

sugar intervention" (e.g. a return of blood glucose level to ≥ 80 mg/dl). See **Section 5.4.1.1 for a List of Low Blood Sugar Interventions.**

Serious Toxicity

3. Any grade 5 toxicity that is deemed by the investigator to be at least possibly attributable to glyburide.
4. Any symptomatic grade 3 or 4 hypoglycemia associated with a non-hematologic grade 3 or greater toxicity that is not resolved with "low blood sugar intervention" (e.g. does not return to blood glucose level to ≥ 80 mg/dl) that is deemed by the investigator to be at least possibly attributable to glyburide. **See Section 5.4.1.1 for a List of Low Blood Sugar Interventions.**

Glyburide will be discontinued for any patient that meets the criteria for either a "**concerning toxicity**" or "**serious toxicity**". These patients will still be evaluable.

Any "**concerning toxicity**" that is observed in at least 6 (of 10 evaluable) patients will trigger a dose reduction (see section 7.1). After 1 dose reduction, if at least 6 (of 10 evaluable) patients are observed to have a "**concerning toxicity**", the study will be terminated.

Any "**serious toxicity**" that is observed in at least 1 (of 10 evaluable) patients will trigger a dose reduction. After 1 dose reduction, if at least 1 (of 10 evaluable) patients is observed to have a "**serious toxicity**", the study will be terminated.

RANDOMIZED PORTION

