If multiple toxicities are seen, the presence of a DLT should be based on the most severe toxicity experienced. Any patient who achieves a DLT will be taken off of the investigational medication immediately, but will still be evaluable.

Concerning Toxicity

1. Any asymptomatic grade 3 or 4 hypoglycemia as defined by CTCAE version 4.0
2. Any non-hematologic grade 3 or greater toxicity (including neurologic toxicity) that is associated with a blood glucose level ≤ 80 mg/dl and is resolved with "low blood sugar intervention" (e.g. a return of blood glucose level to ≥ 80 mg/dl).**See Section 5.4.1.1 for a List of Low Blood Sugar Interventions.**

Serious Toxicity

3. Any grade 5 toxicity that is deemed by the investigator to be at least possibly attributable to the investigational medication.
4. Any symptomatic grade 3 or 4 hypoglycemia that is associated with a non-hematologic grade 3 or greater toxicity that is not resolved with "low blood sugar intervention" (e.g. does not return to blood glucose level of ≥ 80 mg/dl) that is deemed by the investigator to be at least possibly attributable to the investigational medication. **See Section 5.4.1.1 for a List of Low Blood Sugar Interventions.**

Investigational medication will be discontinued for any patient that meets the criteria for a ***“concerning toxicity” or “serious toxicity”***. These patients will still be evaluable. All other patients currently on treatment at the time may continue with their current investigational medication without interruption.

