APPENDIX VII
CTCAE version 4.0 and Toxicity Criteria

This study will utilize **NCI Common Terminology Criteria for Adverse Events (CTCAE) version 4.0 for toxicity and Adverse Event Reporting**. A **grading** (severity) scale is provided for each Adverse Event (AE) term. A copy of the CTCAE version 4.0 can be downloaded from the CTEP web site at: http://ctep.cancer.gov/protocolDevelopment/electronic_applications/ctc.htm. All investigators and study staff have access to a copy of the CTCAE version 4.0. Also, see Sections 5.3 and 7.3 for additional information.

An **Adverse Event (AE)** is any unfavorable and unintended sign (including an abnormal laboratory finding), symptom, or disease temporally associated with the use of a medical treatment or procedure that may or may not be considered related to the medical treatment or procedure.

Grade refers to the severity of the AE. The CTCAE displays Grades 1 through 5 with unique clinical descriptions of severity for each AE based on this general guideline:

- **Grade 1:** *Mild; asymptomatic or mild symptoms; clinical or diagnostic observations only; intervention not indicated.*
- **Grade 2:** *Moderate; minimal, local or noninvasive intervention indicated; limiting age-appropriate instrumental Activities of Daily Living (ADL).*
- **Grade 3:** *Severe or medically significant but not immediately life-threatening; hospitalization or prolongation of hospitalization indicated; disabling; limiting self care Activities of Daily Living (ADL).*
- **Grade 4:** *Life-threatening consequences; urgent intervention indicated.*
- **Grade 5:** *Death related to AE.*

Adverse Event	GRADE				
	1	2	3	4	5
Hypoglycemia	<LLN – 55mg/dL; <LLN – 3.0 mmol/L	<55-40 mg/dL; <3.0-2.2 mmol/L	<40-30 mg/dL; <2.2-1.7 mmol/L	<30 mg/dL; <1.7 mmol/L; life-threatening consequences; seizures	Death

Definition: A disorder characterized by laboratory test results that indicate a low concentration of glucose in the blood.

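### A grade 3+ toxicity at glucose of about 40-80 mg/dl is a dose-limiting toxicity if it resolves with low blood sugar intervention, but falls in neither class if it does not

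*Combined protocol and SAP*

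**What the plan says.** The same two-class definition appears four times: in 5.3.1 (pilot), in 5.3.2 (randomized), and once for each portion in 7.3.4.

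- **Concerning, first item:** asymptomatic grade 3 or 4 hypoglycemia.
- **Concerning, second item:** a non-hematologic grade 3+ toxicity "that is associated with a blood glucose level ≤ 80 mg/dl and is resolved with" low blood sugar intervention. The example given of resolution is glucose returning to at least 80 mg/dl.
- **Serious, first item:** grade 5 toxicity at least possibly attributable to the drug.
- **Serious, second item (pilot wording):** "Any symptomatic grade 3 or 4 hypoglycemia associated with a non-hematologic grade 3 or greater toxicity that is not resolved with" the intervention, and at least possibly attributable. The randomized lists say the same: "Any symptomatic grade 3 or 4 hypoglycemia that is associated with a non-hematologic grade 3 or greater toxicity that is not resolved with" the intervention, with the example "does not return to blood glucose level of ≥ 80 mg/dl".

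Appendix VII puts grade 3 hypoglycemia at below 40 down to 30 mg/dL, and grade 4 at "<30 mg/dL; <1.7 mmol/L; life-threatening consequences; seizures".

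Stopping follows from the class. Section 4.1.9 lists "A dose limiting toxicity (DLT) is reached. See section 5.3.1" and section 4.2.9 lists "A dose limiting toxicity (DLT) is reached. See section 5.3.2"; the only other condition in either place is corticosteroid need before SRS. The pilot primary endpoint (2.3.1) is "Occurrence of Dose Limiting Toxicities (DLTs) between the time of glyburide initiation and the time of the one month follow-up MRI". The absence of a concerning or serious toxicity at the one-week visit permits less glucose testing (4.1.6.4, 4.2.6.4). The pilot count of concerning toxicities sets the randomized testing schedule (5.4.2.2, 5.4.2.3).

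**The concern.** The two classes use different glucose thresholds. The resolved event counts at 80 mg/dl or less. The unresolved event counts only with grade 3 or 4 hypoglycemia. Between about 40 and 80 mg/dl, the patient who recovers after taking sugar must stop the drug, while the patient who does not recover meets no definition. A rule meant to rank severity treats the worse course more leniently.

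At stake for that patient are a mandated stop and continued routine glucose testing. At stake for the pilot is a concerning count that omits the event, both for the 6-of-10 dose rule and for the choice between lighter and fuller monitoring in the randomized portion. Section 1.9 itself states that oral glyburide has not been shown to be safe in non-diabetic people, so the definition should be complete.

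**Working it through.** **1. Classification.** Take a symptomatic, non-fatal, non-hematologic grade 3 or 4 toxicity, at least possibly attributable to the drug, and apply the four items with the Appendix VII grades.

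| Glucose (mg/dl) | Resolves | Does not resolve |
|---|---|---|
| 25, 35 | concerning | serious |
| 40, 50, 60, 80 | concerning | neither |
| 40 to 80, graded as grade 4 hypoglycemia for seizure or life-threatening consequences | concerning | serious |

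In the middle row, the unresolved event fails each item for a different reason. It is not grade 3 or 4 hypoglycemia (first concerning item). It did not resolve (second concerning item). It is not fatal (first serious item). It lacks symptomatic grade 3 or 4 hypoglycemia (second serious item).

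**2. The plan's own figures (9.5.1), exact binomial, n = 10.** All four reproduce:
- at least 1 serious at 30%: 1 - 0.7^10 = 0.9718 (stated 97%)
- no event at 1%: 0.99^10 = 0.9044 (stated 90%)
- at most 5 concerning at 30%: 0.9527 (stated 95%)
- at least 6 concerning at 70%: 0.8497 (stated 85%)

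**3. Chance that the unclassed event occurs.** The documents give no rate, so 1% to 5% per patient is an assumption.
- 10 pilot patients: 1 - 0.99^10 = 9.6%; 1 - 0.95^10 = 40.1%
- 20 randomized glyburide patients: 1 - 0.99^20 = 18.2%; 1 - 0.95^20 = 64.2%

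These are chances that an event happens, not that a decision changes.

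**4. Effect on the pilot counts.** Let b be the rate of classed concerning toxicity and q the rate of the unclassed event, with at most one of the two per patient. The recorded count is X ~ Bin(10, b) and the true count is T ~ Bin(10, b + q). Since X never exceeds T, P(X ≤ c and T > c) = P(X ≤ c) - P(T ≤ c). For example, with b = 30%, q = 5% and c = 5: 0.9527 - 0.9051 = 0.0476.

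| b | q | True ≥ 6, recorded ≤ 5 | True ≥ 4, recorded ≤ 3 |
|---|---|---|---|
| 10% | 1% | 0.01% | 0.5% |
| 30% | 1% | 0.8% | 2.7% |
| 10% | 5% | 0.1% | 3.7% |
| 30% | 5% | 4.8% | 13.6% |

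The unclassed events alone would reach 6 of 10 with probability 0.015% even at 10% per patient. The last column affects only how often randomized patients test glucose. Only events from SRS onward bear on the counts, because 7.1.4 makes a patient with a DLT before SRS inevaluable; q should be read in that sense.

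**5. One patient.** Suppose the event falls between SRS and the one-week visit. The drug may then continue to the one-month MRI: 30 - 7 = 23 days, or 25 - 10 = 15 to 40 - 4 = 36 days with the visit windows. Routine self-testing may fall from 4 to 1 per day (pilot) or from 1 to 0 (randomized, once-daily schedule).

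**The case against.** The best defence is that resolution serves as an attribution test. The second concerning item has no attribution clause, so response to sugar is what ties the toxicity to low glucose. In patients with brain metastases receiving SRS, a grade 3 neurologic event at 75 mg/dl that ignores sugar may come from tumor or radiation. Nor is 80 mg/dl low by the protocol's own standards: eligibility accepts glucose of 80 mg/dL or more (3.1.8), and the pre-meal target is 80-130 (Appendix II). This stands as a reason to require attribution, but it does not remove the gap. The protocol's example of non-resolution is glucose that fails to recover, and 5.4.1 sends exactly that patient to the study team and/or 911.

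Three narrowing points also stand:
- If resolution means only that glucose returns to 80 mg/dl, a toxicity that persists after glucose recovers is already concerning. The gap is then persistently low glucose, after an intervention that is itself repeated (5.4.1.1).
- Seizures or life-threatening consequences can be graded as grade 4 hypoglycemia and so count as serious. A reader might infer that every unresolved grade 3+ event escapes; Appendix VII does not support that.
- Backstops exist: investigator judgment, extra testing for symptoms (Appendix II), grade 2-5 toxicity as a pilot secondary endpoint (2.4.1.2), adverse event and 24-hour serious event reporting (7.3.1, 7.3.3), committee review of all pilot data (5.2), and coming off treatment if unblinded (7.6.3). None of them assigns a DLT class or corrects the count.

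**Conclusion.** The safety rule is wrong as written and cheap to improve. The gap covers a non-fatal, non-hematologic grade 3+ toxicity at about 40-80 mg/dl that does not resolve, excluding events graded as grade 4 hypoglycemia for seizures or life-threatening consequences. The main effect is on stopping and monitoring the individual patient. The randomized portion has no count rule, so there that is the whole effect.

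Three stronger inferences are not supported:
- **That the 6-of-10 rule is undermined.** At an assumed 1% the result changes with probability 0.01% to 0.8%; even at 5% it is at most 4.8%, for classed rates of 10% to 30%.
- **That patients would be kept on drug.** The rules permit the further 15 to 36 days; they do not require them.
- **That unresolved symptomatic grade 3 or 4 hypoglycemia with no other grade 3+ toxicity is also unclassed.** This depends on the reading. If the hypoglycemia itself counts as the associated toxicity, and is attributable, the event is already serious.

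The classification follows from the text alone. Every probability for the unclassed event rests on assumed rates.

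**What to change.** Keep the present items and add a third concerning item to all four lists (5.3.1, 5.3.2 and both portions of 7.3.4):

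*Any non-hematologic grade 3 or greater toxicity associated with a blood glucose level ≤ 80 mg/dl that is not resolved with low blood sugar intervention, is at least possibly attributable to glyburide [randomized portion: the investigational medication], and does not meet the definition of a serious toxicity.*

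Do not name symptomatic grade 3 or 4 hypoglycemia in this item. On one reading that unresolved event is already serious, and naming it here would invite moving it from a 1-of-10 trigger to a 6-of-10 trigger.

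The cost is one item in four lists. A few more events may count as concerning and stop the drug, which the attribution clause limits. If the added events raise the concerning rate from 30% to an assumed 31% or 35%, the chance of at most 5 in 10, and so of being declared tolerable, falls from 95.3% to 94.5% or 90.5%. The new item asks for attribution where the resolved item does not; that difference is deliberate, because an unresolved event lacks the response to sugar that otherwise links it to low glucose.
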